10.6.2 Secondary Efficacy Objectives

10.6.2.1 Analyses of NS-065/NCNP-01 patients only

TTRW, TTCLIMB, NSAA, 6MWT and QMT will be summarized by dose level over time using descriptive statistics. Actual values and change from the Pre-Infusion Visit (baseline from Study NS-065/NCNP-01-201) and change from Week 25 (baseline of the NS-065/NCNP-01-202 study) will be presented.

The TTRW and TTCLIMB times to perform the test will also be converted to velocities. For a test that the patient could not perform, the velocity will be set to zero. If needed, a data transformation or nonparametric approach will be performed for these assessments. Within patient changes and velocities (possibly transformed) will be tested using a one-sided paired t-test within dose group and within both dose groups combined.

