1.2.1. Glucocorticoid Treatment

At present, treatment with glucocorticoid (GC) medication is the only pharmacological intervention that has been shown to slow the decline of strength and function in DMD patients. The two main GCs used in DMD are prednisone and deflazacort (EMFLAZATM). Daily oral administration of prednisone or deflazacort stabilizes or improves strength and prolongs ambulation (6-11). The mechanism by which GCs are beneficial in dystrophin deficiency is likely multifactorial, including anti-inflammatory actions. The immunosuppressive effects of GCs may not be beneficial, and other immunosuppressants have not shown benefit (8).

In 2005, the American Academy of Neurology issued a practice parameter regarding GC treatment in DMD and recommended that GC should be offered as treatment, despite known side effects (12). The significant side effects of GCs include cushingoid features, adverse behavioral changes, obesity, growth retardation, increased risk for bone fractures, gastritis, delayed puberty, cataracts, hypertension, glucose intolerance, susceptibility to infection, and masking of response to stress (13). On February 9, 2017, the United States Food and Drug Administration (FDA) approved EMFLAZATM to treat patients 5 years of age and older with DMD.

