10. PLANNED STATISTICAL METHODS

10.1 General Considerations

The statistical analyses described in this section will be performed as further outlined in the Statistical Analysis Plan (SAP), which will be finalized prior to database lock. The SAP will supersede the protocol if there are any differences between the two documents in the plans for data analysis and the differences will be noted in the SAP. The SAP will be included as an appendix in the clinical study report for this protocol. Statistical analyses will be performed using SAS 9.4 or higher.

Patients will be enrolled in this study after completing Study NS-065/NCNP-01-201 and will continue with the study dose (40 mg/kg/week or 80 mg/kg/week) they received in Study NS-065/NCNP-01-201. Results for this study will be summarized by study dose.

Statistical analyses will occur at the following times:

- Every 6 months. A report for the DSMB will be produced including all safety data available at the temporary data lock. A template report will be provided to the DSMB prior to the first report, and the report formats will be updated at the DSMB's requests as the data develop. The DSMB will review completeness of efficacy data, but will not review the efficacy data itself.
- At the conclusion of the study. A summary report will be generated on all baseline characteristics, safety assessments and efficacy assessments, addressing each of the primary, secondary and exploratory objectives of the study.

All statistical tests will be performed at a two-sided significance level of 0.05 with no corrections for multiple comparisons or multiple outcomes. Note however, that since this is an early phase extension study, with a focus on safety, the emphasis will not be on statistical tests (i.e., p-values).

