10.6.1 Primary Efficacy Objective

The primary efficacy outcome measure (TTSTAND) will be summarized by dose level over time using descriptive statistics. Actual values and change from the Pre-Infusion Visit (baseline from Study NS-065/NCNP-01-201) and change from Week 25 (baseline of the NS-065/NCNP-01-202 study) will be presented.

The TTSTAND times to perform the test will also be converted to velocities. (Note that a test result that is to be converted to velocity that the patient could not perform due to disease progression will have velocity set to zero only at the first visit where this occurs. After that visit, missing observations due to disease progression will be left as missing.). If needed, a data transformation or nonparametric approach will be performed for these assessments. Within patient changes and velocities (possibly transformed) will be tested using a one-sided paired t-test within dose level and within both dose groups combined.

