10.8 Handling of Missing Data

Every effort will be made to collect all data. However, despite best efforts, missing or incomplete data may be reported. All missing or partial data will be presented in the patient data listing, as they are recorded on the eCRF.

Patients lost to follow-up or withdrawn will be included in statistical analyses up to the point of their last evaluation. Unless otherwise specified, no imputation of values for missing data will be performed. Of note, since patients with DMD are expected to decline over time, imputing efficacy parameters by last value carried forward mostly biases towards patients appearing stronger or faster than they are, since it carries forward potentially a better value than the value at the time of the missed observation. Therefore, for this study, we will summarize how much data are missing, but do not expect to need to impute any data to accomplish the analyses as described. Details of handling missing data will be described in the Statistical Analysis Plan.

Missed assessments which occurred as a result of the COVID-19 pandemic will be entered on the COVID-19 Protocol Deviation Log by site personnel. It is anticipated that some or all assessments and laboratory tests required by the protocol schedule of events may be missed during the pandemic. Some of the missed assessments may be able to be collected at the next home or onsite visit. The missing data will be summarized in the Statistical Analysis Plan.

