Neither NS Pharma nor a service provider contracted to analyze data and complete the study report is permitted to interpret a blank answer; therefore, all fields should be complete. All requested information must be entered on the eCRFs. If an item is not available or is not applicable, this fact should be indicated as (N/A) not available or (N/D) not done; do not leave a space blank.

It is essential that all dates appearing on NS Pharma patient data collection forms for laboratory tests, cultures, etc., be the dates on which the specimens were obtained, or the procedures performed. The eCRFs will be electronically signed by the Investigator and dated as verification of the accuracy of the recorded data. All data collection forms should be complete within 48 hours following the evaluation.

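### The zero-velocity rule is tied to disease progression in section 10.6.1 but carries no condition on cause in 10.6.2.1 and 10.6.2.2, so a temporary inability can be scored as loss of the skill

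*Combined protocol and SAP*

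**What the plan says.** Three places in protocol section 10 turn a failed timed test into a number.

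- **10.6.1 (TTSTAND, treated boys only):** a test the boy "could not perform due to disease progression will have velocity set to zero only at the first visit where this occurs". Later observations missing because of progression stay missing.
- **10.6.2.1 (TTRW and TTCLIMB, treated boys only):** "For a test that the patient could not perform, the velocity will be set to zero". No cause is named.
- **10.6.2.2 (TTSTAND, TTRW and TTCLIMB against DNHS):** the same sentence as in 10.6.2.1, again with no cause, and now covering TTSTAND.

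The general default in 10.8 is: "Unless otherwise specified, no imputation of values for missing data will be performed". It adds: "Details of handling missing data will be described in the Statistical Analysis Plan". Section 10.1 gives that document precedence: "The SAP will supersede the protocol if there are any differences between the two documents in the plans for data analysis". The supplied document contains no separate SAP text beyond section 10.

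On data capture, section 11.8 says: "If an item is not available or is not applicable, this fact should be indicated as (N/A) not available or (N/D) not done". It does not ask why a test was not done. Sections 7.14.1 to 7.14.3 list no reason for non-performance among the recorded items.

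**The concern.** Zero is the floor of the velocity scale and is meant to represent lost function. A boy in a cast, or recovering from an operation, has not lost the skill. If he is scored zero, his velocity drops to the floor and then jumps back when he recovers. In a paired analysis that is an outlier. In a mixed model it is a false dip and recovery.

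Such visits are foreseeable. Stable glucocorticoid treatment is an inclusion criterion (4.2), and section 1.2.1 lists "increased risk for bone fractures" among its side effects. Section 7.14.2 says the run/walk test can be associated with falls, though infrequently reported. Surgically placed ports may be approved (3.2.2, 9.13). Function is tested at 16 extension visits from Week 37 to Week 217, so about 16 boys give up to 16 × 16 = 256 boy-visits.

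The matter reaches a primary objective. Primary objective 2 compares TTSTAND with matched historical controls, and that comparison is specified only in 10.6.2.2, under the unconditional sentence. There, a false zero in a treated boy counts against the drug and one in a control counts in its favour.

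**Working it through.** **Text.** The plan gives no figure to reproduce, so the first check is the wording.

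| Analysis | Section | Zero limited to progression? |
|---|---|---|
| TTSTAND, treated only | 10.6.1 | Yes |
| TTRW, TTCLIMB, treated only | 10.6.2.1 | Not stated |
| TTSTAND, TTRW, TTCLIMB vs DNHS | 10.6.2.2 | Not stated |

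The default in 10.8 does not close the gap: it yields wherever something else is specified, and the zero rule is such a specification. The same TTSTAND visit, missed through injury, would therefore be missing under 10.6.1 and could be zero under 10.6.2.2. (10.6.1 also limits the zero to the first such visit and the other two sections do not. That is a separate difference; this point concerns cause.)

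**Size, by illustration.** About 16 boys in total comes from 10.2. Assumed, because the documents do not give them:

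- 8 boys per dose group
- true velocity v of 1.0 to 2.0 m/s
- SD of change s of 0.2 to 0.4 m/s in the unaffected boys, with mean change 0

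One boy with no true change is scored 0, so his recorded change is -v.

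*Shift in mean change* = -v/n.
- n=8: -1.0/8 = -0.125 to -2.0/8 = -0.25 m/s
- n=16: -1.0/16 = -0.0625 to -2.0/16 = -0.125 m/s

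If he has the group-average velocity, this is 1/8 = 12.5% or 1/16 = 6.25% of the group mean.

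*Standard error at n=8.* The sum of squares with the zero is 6s² + (7/8)v².
- v=2.0, s=0.2: 0.24 + 3.50 = 3.74; SD = √(3.74/7) = 0.73; SE = 0.73/√8 = 0.258
- v=1.0, s=0.4: 0.96 + 0.875 = 1.835; SD = √(1.835/7) = 0.51; SE = 0.51/√8 = 0.181

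There are two reasonable comparators:
- *The boy is tested and shows no change (n=8).* The sum of squares is 6s², so the ratio is √[(6s² + 0.875v²)/6s²]: √(3.74/0.24) = 3.95 and √(1.835/0.96) = 1.38.
- *The boy is left missing (n=7).* The SE is s/√7, which is 0.076 or 0.151, so the ratio is 0.258/0.076 ≈ 3.4 or 0.181/0.151 ≈ 1.2.

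At n=16, against the first comparator, the ratio is √[(14s² + (15/16)v²)/14s²]: √(4.31/0.56) = 2.77 for v=2.0, s=0.2, and √(3.1775/2.24) = 1.19 for v=1.0, s=0.4.

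*Sign of the result.* With v=2.0 at n=8, any mean gain in the other seven boys below 2.0/7 = 0.29 m/s becomes an apparent group loss.

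**The case against.** A reader might infer that the plan orders a zero for every test not completed, whatever the reason, so that a fracture is certain to be scored as complete loss. The documents do not go that far.

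- **Silence on cause.** 10.6.2.1 and 10.6.2.2 say nothing about cause; they do not say that all causes count. Refusal, or an equipment or visit problem, is not naturally an inability of the patient, and pandemic-related misses have their own log (10.8).
- **A not-done code exists.** A boy in a cast who is never tested could be entered as not done and left missing. This stands in part: nothing marks the border between not done and could not perform.
- **10.6.1 may be the general rule.** Its note is worded for any result being converted to a velocity, not for TTSTAND by name, so the later sentences could be shorthand for it. That is plausible but not certain, because the note sits in the TTSTAND section and the later sections restate the rule without the condition.
- **The SAP may settle it.** It takes precedence and was to hold the missing-data details. Its text cannot be checked here.
- **Robust methods are available.** 10.6.2.1 allows a transformation or nonparametric approach if needed, and 10.1 plays down p-values. A signed-rank test would dampen one extreme value, but the recovering boy would still rank as a large decline and the descriptive means would still move. 10.6.2.2 does not repeat the option.

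A reader might also take the roughly fourfold SE inflation as typical. It is the top of an assumed range.

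**Conclusion.** The inconsistency is real and worth correcting. The progression condition appears once and is absent from two later statements of the same rule, one of which governs the TTSTAND comparison named in primary objective 2. Followed literally, those statements give a wrong value for temporary inability from injury, surgery or acute illness. The fair description is an unconditional and ambiguous rule, not a proven instruction to score every cause as zero.

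On the assumed inputs, one misclassified visit is material in groups this small, in both the mean and the standard error. How often it would happen is unknown, since the documents give no injury rate. The textual conflict over TTSTAND depends on none of these assumptions.

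**What to change.** 1. In 10.6.2.1 and 10.6.2.2, or in the SAP that overrides them, set velocity to zero only for inability due to disease progression. Leave inability from injury, surgery or acute illness missing.
2. Take the reason from source documents or the eCRF, and add a reason code if none exists. State how a test recorded as not done differs from one the boy could not perform.
3. Apply the same classification to DNHS, and state how unclassified DNHS inability is handled in the main analysis.
4. Run sensitivity analyses in both directions: unclassified DNHS inability counted as progression, and the same cases left missing. The first alone would lower control velocity and so favour the drug.

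The cost is one clause in two sentences, possibly one field on the function page, and two sensitivity runs. Applying 10.6.1 already requires knowing whether progression was the cause, so the reason may already be on record. If it is not, this is a late amendment (version 11.0, July 2020) and some reasons would need retrospective review. Some may be unavailable in DNHS, which is why step 4 is needed.

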10.6.2.2 Analyses comparing NS-065/NCNP-01 patients to historical controls

A matched data set from the CINRG DNHS data will be created. The purpose of the matching is to create a group data set that corresponds in characteristics to the patients in this study. The CINRG DNHS data set includes patients from age 2 years to over 30 years old, and some have been followed for close to a decade. Therefore, it is important to create a comparator group which will allow valid group comparisons. No patient to patient matched analysis is proposed. The sole purpose of the matching is to create a historical control group which is comparable in its basic characteristics to the study patient group. The final CINRG DNHS data set is expected to have between 16 and 32 patients included with time intervals of evaluations between 6 and 15 months. TTSTAND, TTRW, TTCLIMB, NSAA, 6MWT, and QMT results will be compared between the NS-065/NCNP-01 patients and the CINRG DNHS patients possibly using mixed-effects linear

models. The TTSTAND, TTRW, and TTCLIMB times to perform the test will be converted to velocities. For a test that the patient could not perform, the velocity will be set to zero.

10.7 Interim Analyses

Safety analyses are planned every 6 months as described above. Moreover, semi-annual reports to the DSMB will be descriptive and focus on safety.

In addition, interim analyses for safety are planned and interim analyses for efficacy may be conducted and further described in the Statistical Analysis Plan.

10.8 Handling of Missing Data

Every effort will be made to collect all data. However, despite best efforts, missing or incomplete data may be reported. All missing or partial data will be presented in the patient data listing, as they are recorded on the eCRF.

Patients lost to follow-up or withdrawn will be included in statistical analyses up to the point of their last evaluation. Unless otherwise specified, no imputation of values for missing data will be performed. Of note, since patients with DMD are expected to decline over time, imputing efficacy parameters by last value carried forward mostly biases towards patients appearing stronger or faster than they are, since it carries forward potentially a better value than the value at the time of the missed observation. Therefore, for this study, we will summarize how much data are missing, but do not expect to need to impute any data to accomplish the analyses as described. Details of handling missing data will be described in the Statistical Analysis Plan.

Missed assessments which occurred as a result of the COVID-19 pandemic will be entered on the COVID-19 Protocol Deviation Log by site personnel. It is anticipated that some or all assessments and laboratory tests required by the protocol schedule of events may be missed during the pandemic. Some of the missed assessments may be able to be collected at the next home or onsite visit. The missing data will be summarized in the Statistical Analysis Plan.

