7.14.4. North Star Ambulatory Assessment (NSAA)

NSAA will be performed by a CE at visits specified in the schedule of study assessments (Table 1). The NSAA is a clinician rated, 17-item, functional scale originally designed for ambulant boys with DMD who are able to ambulate at least 10 meters (24). This evaluation tool assesses functional activities including standing, getting up from the floor, negotiating steps, hopping, and running. The assessment is based on a 3-point rating scale of 2 = ability to perform the test normally, 1 = modified method or assistance to perform test, 0 = unable to perform the test. Thus, total score can range from 0 (completely non-ambulant) to 34 no impairment on these assessments. Individual test item scores and total score will be recorded in source documents and in the relevant eCRF. This test should take approximately 10 minutes and is not associated with any risks. The NSAA should be administered before the 6MWT at each occurrence.

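### The plan assigns no 6MWT value to a boy who can no longer walk, so its no-imputation default would leave non-walkers out of the 6MWT summaries and the control comparison

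*Combined protocol and SAP*

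**What the plan says.** The general rule is in section 10.8: "Unless otherwise specified, no imputation of values for missing data will be performed". On boys who leave the study, the same section says: "Patients lost to follow-up or withdrawn will be included in statistical analyses up to the point of their last evaluation". It then defers: "Details of handling missing data will be described in the Statistical Analysis Plan". The combined document contains no SAP text on this point.

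The exceptions for inability concern velocities only:

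- **TTRW and TTCLIMB**, section 10.6.2.1: "For a test that the patient could not perform, the velocity will be set to zero".
- **TTSTAND, TTRW and TTCLIMB against controls**, section 10.6.2.2: the same zero-velocity rule.
- **TTSTAND within treated boys**, section 10.6.1: zero velocity at the first failed visit only, and missing afterwards.

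The 6MWT is a distance, and none of these rules names it. Section 7.14.5 says only that the metres walked in six minutes are recorded. Sections 10.6.2.1 and 10.6.2.2 nevertheless list the 6MWT among the outcomes to be summarised by dose level over time and compared with the natural history (DNHS) controls.

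The NSAA is different. Section 7.14.4 scores an item "0 = unable to perform the test" and states that the "total score can range from 0 (completely non-ambulant) to 34".

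**The concern.** Loss of ambulation is foreseeable here. Boys entered Study 201 at 4 to under 10 years (section 1.3.5.2) and may be treated for 216 weeks across both studies. Sections 7.6 and 7.14.7 already plan for non-ambulant boys when height is measured.

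If such a boy has no 6MWT value, the reason is the outcome itself. The summaries then describe only those still walking and overstate the function of the group. Two features of the plan make this more than an omitted detail:

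- **Inconsistency between outcomes.** At one visit the same boy would count as zero in TTRW velocity and be absent from 6MWT. The two outcomes could then disagree for a purely analytic reason.
- **Conflict with the plan's own reasoning.** Section 10.8 rejects last value carried forward because it makes boys look stronger or faster than they are. Omitting non-walkers biases the mean in the same direction.

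Timing also matters. The study is open-label (section 5.4), and section 10.1 requires only that the SAP be final before database lock. A coding rule settled late could be chosen knowing which boys had stopped walking.

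**Working it through.** **1. How an untested boy is likely to be coded.** Section 11.8 tells sites to mark an item as not available or not done and bars analysts from interpreting a blank. Section 10.6.1 itself describes inability through progression as a missing observation. The authors also thought a zero rule had to be written for TTRW and TTCLIMB. Together these make missing the more natural coding for an unperformed 6MWT, although section 7.14.5 does not exclude 0 m.

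**2. NSAA check.** Section 7.14.4 gives 17 items scored 0 to 2. The range is 17 × 0 = 0 to 17 × 2 = 34, which reproduces the stated range. A non-ambulant boy has an observed score of 0, so the default in section 10.8 does not reach him if he is tested.

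**3. Age at the end.** 216 × 7 / 365.25 = 4.14 years, so ages 4 to under 10 become about 8.1 to 14.1.

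**4. Size of the bias in the 6MWT mean.** Let n boys attend, let k be unable to walk, and let M be the mean of those still walking.

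- Mean with non-walkers left out: M
- Mean with non-walkers at 0 m: M(n−k)/n
- Ratio: n/(n−k). Difference: Mk/n.

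Inputs: n = 16 (section 10.2). The values of k and M = 350 m are assumptions, because the documents give neither a rate of loss of ambulation nor any 6MWT results.

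| k of 16 | n/(n−k) | Overstatement | Mean with zeros if M = 350 m | Difference |
|---|---|---|---|---|
| 1 | 1.067 | 6.7% | 328 m | 22 m |
| 2 | 1.143 | 14.3% | 306 m | 44 m |
| 3 | 1.231 | 23.1% | 284 m | 66 m |
| 4 | 1.333 | 33.3% | 263 m | 88 m |

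For M between 300 and 400 m the difference is 38 to 50 m at k = 2 and 75 to 100 m at k = 4. Summaries are by dose level. With an assumed 8 boys per group, one non-walker gives 8/7 (14.3%) and two give 8/6 (33.3%).

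**5. Does the mean have to rise?** Suppose all 16 boys averaged 350 m at the previous visit, and 2 boys whose last value was L then leave. With no decline in the other 14, the observed mean rises by 2(350−L)/14: 36 m for L = 100 and 21 m for L = 200. If the other 14 decline by more than that on average, the observed mean falls. The bias is upward in either case, but the trend can go either way.

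**6. Comparison with controls.** Let p_T and p_C be the shares unable to walk in the treated and control groups. If both groups' walkers average 350 m and non-walkers are left out of both, the treated-minus-control difference is shifted by 350(p_T − p_C).

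- p_T = 2/16 and p_C = 4/16: 350 × (−0.125) = −44 m, against the drug.
- Shares reversed: +44 m, in its favour.
- Equal shares of 2/16, with controls coded 0 m and trial boys coded missing: 350 − 306 = 44 m in favour of the drug, from coding alone.

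These shares are illustrative.

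**The case against.** The strongest reply is that the documents are silent rather than wrong. Section 7.14.5 can be read as recording 0 m for a boy who walks no distance, and section 10.8 expressly sends the details to the SAP, which section 10.1 says overrides the protocol. This stands in part: exclusion of non-walkers from 6MWT is not stated by name, and SAP text not included here may already settle it. It does not remove the point, because the written default applied to a result marked not done gives a survivor-only mean.

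Several stronger readings are tempting, and the documents do not support them.

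- **That NSAA has the same gap.** It does not, because section 7.14.4 already supplies the zero. One uncertainty remains: "The NSAA is a clinician rated, 17-item, functional scale originally designed for ambulant boys with DMD", so sites might stop administering it once a boy cannot walk.
- **That 6MWT results will appear to improve as boys decline.** Step 5 shows that the mean is biased upward but need not rise.
- **That the control comparison will favour the drug.** Step 6 shows that the direction depends on losses in each group and on using the same coding in both.
- **That a paired test on 6MWT is biased.** In section 10.6.2.1 the paired t-test sentence closes the paragraph on TTRW and TTCLIMB velocities. Whether it extends to 6MWT is unclear.

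A mixed model would reduce the problem only if missingness depended on observed values, and section 10.6.2.2 describes its use only as possible.

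It is also fair to say that 6MWT is a secondary outcome in about 16 boys, that section 10.1 plays down statistical tests, and that section 10.8 promises a summary of the amount of missing data. These limit the weight of the point. A count of missing values would not by itself separate inability from a missed visit.

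**Conclusion.** The point holds for 6MWT only. The plan gives zero to a boy who cannot do TTRW or TTCLIMB but assigns no value to his 6MWT, so the default leaves him out unless a site happens to enter 0 m. If k of n are omitted, the mean is overstated by a factor of n/(n−k), which is 6.7% to 33.3% for 1 to 4 of 16.

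This rests on three assumptions: that inability is entered as missing, that 0 m is the proper value for a boy who cannot walk, and the values of k. The figures in metres also depend on the assumed mean among walkers. No direction is claimed for the trend over time or for the control comparison. It is worth correcting, but it does not touch the primary efficacy measure.

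**What to change.** Add to sections 10.6.2.1 and 10.6.2.2, and carry into the SAP:

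1. 6MWT distance is 0 m at every attended visit where disease progression prevents walking.
2. The same rule applies to the DNHS controls wherever inability can be identified. Where it cannot, say so and report how many values are affected.
3. Values missing for other reasons (missed visit, COVID-19, temporary injury, withdrawal) stay missing.
4. The number unable to perform the test is reported at each visit, by dose level and for controls.
5. A rank-based sensitivity analysis accompanies the means.
6. NSAA continues to be scored after loss of ambulation, using the zero that section 7.14.4 already defines.

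The cost is a few sentences of plan text and a reliable record of why a test was not done. Section 11.8 describes only not-available and not-done codes, so that reason may have to be taken from source documents. Zeros skew the distribution, which is a small drawback that the rank-based analysis addresses. The rule does not help with boys who withdraw after losing ambulation, so their number should be reported as well. Fixing the text before the 6MWT data are reviewed prevents the rule from being chosen in the light of who has stopped walking.
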